5.1.1 EmitBio™ RD-X19 Device Characteristics

Table 2.

Characteristic	Target
Route of Administration	Oral Illumination
Device Configuration	Hand-held, rechargeable
Target Exposure Area	Oropharynx and surrounding tissues
Depth of Tissue Penetration	< 0.5 mm
Temperature (IEC 60601-1)	< 48 °C (for durations <10 min)
*	

5.2 Risk/Benefit Assessment

5.2.1 Known Potential Risks

The potential risks of participating in this trial are those associated with having blood drawn and mild, transient, local reactions as measured in RD19-01-3Q20, a Phase I Open Label, Acute Safety Study of the EmitBio™ RD-X19 Device.

Drawing blood may cause transient discomfort and fainting. Fainting is usually transient and managed by having the subject lie down and elevate his/her legs. Bruising at the blood draw site may occur but can be prevented or lessened by applying pressure to the blood draw site for a few minutes after the blood is taken.

Extensive evaluation of the RD-X19 and similar energy-based devices routinely used for oral and skin care purposes resulted in the Sponsor, after careful consideration, making the determination that RD-X19 was a “Not Significant Risk” (NSR) device per FDA guidelines.

Eye exposure is to be avoided. Direct illumination of unprotected eyes can result in damage to the retina, and especially the macula. Other eye structures can also experience thermal injury. Study staff must ensure volunteers understand to never point the RD-X19 device toward their or anyone else's eyes.

RD19-01-3Q20 Phase I Trial

This was a first-in-man Phase I study that evaluated the acute safety and tolerability of the RD-X19 device among 25 healthy volunteers between the ages of 18 and 45. A single dose [REDACTED] and schedule ([REDACTED])

[REDACTED] was evaluated for 14 consecutive days. In total, subjects received a weekly dose of [REDACTED] per week for a time weighted average of [REDACTED].

No SAEs were observed during the study. No AEs based on laboratory findings were observed during the study.

Twelve (12) study subjects reported a total of 3 distinct AE terms (local site reaction, headache, nausea) and 23 total AEs. Of the 23 total AEs, 22 were classified as mild (grade 1) with a single headache classified as moderate (grade 2). No AE required treatment or alteration to the study subject's participation in the trial. No study subject withdrew from the trial because of an AE.

All AEs were of short duration, with resolution typically reached the same day or within 24 hours. Since study subjects used the RD-X19 device approximately every 12 hours for 14 contiguous days, there was a continuous temporal association with RD-X19 device use and incident AEs during the course of RD19-01-3Q20. By definition, all local site reactions were attributed to the device; all were mild and transient and there was no pattern of increasing frequency with repeated, cumulative dosing.

Population-based epidemiological data for headaches and nausea were considered when establishing device attribution. Approximately 40% of the general adult population have weekly headache and over 30% suffer from intermittent bouts of nausea of unknown origin. Given the frequencies of headache and nausea reported in RD19-01-3Q20 are less than those reported in population-based epidemiological studies, the relationship with the RD-X19 device cannot be determined.

In summary, the RD19-01-3Q20 Phase I trial demonstrated that EmitBio™ RD-X19 is a safe device, consistent with the sponsor's and IRB's original conclusion that RD-X19 is a NSR device.

Risks to Privacy

Subjects will be asked to provide personal health information (PHI). All attempts will be made to keep this PHI confidential within the limits of the law. However, there is a chance that unauthorized persons will see the subject's PHI. All study records will be kept in a locked file cabinet or maintained in a locked room at the participating clinical trial site(s). Electronic files will be password protected. Only people who are involved in the conduct, oversight, monitoring, or auditing of this trial will be allowed access to the PHI that is collected. Any publications from this trial will not use information that will identify subjects by name.

Organizations that may inspect and/or copy research records maintained at the participating clinical trial site(s) for quality assurance (QA) and data analysis include groups such as the IRB and the FDA.

A description of this clinical trial will be posted on <http://www.ClinicalTrials.gov>. This web site does not include information that can identify subjects.

There may be other risks, discomforts or side effects that are entirely unknown at this time.

5.2.2 Known Potential Benefits

There is no guaranteed benefit to study participants. Use of EmitBio™ RD-X19 is intended to reduce viral load of SARS-CoV-2 and alleviate the symptoms associated with uncomplicated COVID-19. There is also the potential for benefit to society resulting from insights gained from

participation in this study due to the widespread, and accelerating, threat of SARS-CoV-2 and COVID-19.

6 STUDY DESIGN

[figure not shown]
6.1 Overall Design

Volunteers will provide informed consent prior to initiating any screening procedures. Those meeting all screening criteria will be eligible for enrollment and randomization into the study. Study subjects will be enrolled into treatment and control arms within two cohorts:

Volunteers meeting all inclusion criteria and none of the exclusion criteria will be randomized to the RD-X19 treatment arm or the sham treatment arm within each cohort. Study subjects will be randomized in a 2:1 ratio (20 RD-X19 : 10 sham) per dose cohort. The double-blind, sham-controlled period will last 8 days. Assessments of study subjects will occur on study days 1, 2, 3, 5 and the final assessment visit on Day 8. Since CMP and CBC results will not be available until study day 2, all volunteers who have significant abnormalities will be immediately contacted and advised of the abnormality, discontinued from active participation in the protocol and advised regarding appropriate medical follow-up outside the study. All such study subjects will be replaced with a new volunteer. This is a randomized, adaptive, group sequential dose finding study. The primary goal of the study is to evaluate the efficacy and safety of the RD-X19 device in SARS-CoV-2 infected individuals with outpatient COVID-19. The primary efficacy outcome is the time weighted average change in SARS-CoV-2 viral load assessed via RT-qPCR. Safety assessment will include the incidence of device-related serious adverse events or patterns of severity ≥ 2 device-related adverse events.

Figure 1: Study Design

The interim analysis at the conclusion of Cohort 1 will consist of the following evaluations:

- A planned efficacy evaluation of the time weighted average change in SARS-CoV-2 viral load from baseline will be conducted as an assessment of benefit to the subjects.
- Safety evaluations, performed by a ~~independent~~ safety monitoring team as outlined in the committee charter, are to ensure that each dose level under evaluation is safe through 4 days of treatment. Specific criteria for safety review will include:
 - Number of subjects experiencing laryngospasm, bronchospasm or anaphylaxis within 2 hours after use of the RD-X19 Device that is considered related to RD-X19.
 - Number of subjects experiencing an allergic reaction such as generalized urticaria (defined as occurring at three or more body parts) within 72 hours after administration of light that is considered related to RD-X19.
 - Number of subjects experiencing an SAE or Grade 3 AE, in the same SOC grouping of Preferred Terms based on Medical Dictionary for Regulatory Activities (MedDRA) coding, considered to be related to RD-X19.

Safety and tolerability (local reactogenicity) will be assessed actively on each clinic visit by review of potential adverse events (AEs) and targeted physical examination, as required. Volunteers will be encouraged to contact designated clinical trial staff for AEs of a medically-urgent nature as soon as is practically possible and to seek immediate medical care, if needed.

Metabolic, liver, kidney and hematological laboratory evaluations will be performed at screening and at Day 8 or early termination (and potentially during unscheduled) clinic visits.

Study Subject safety will be monitored throughout the study by the Investigator and supported by regular review by the Medical Monitor and an external Data Monitoring Committee.

6.2 Objectives and Endpoints

Table 1: Objectives and Endpoints (Outcome Measures)

OBJECTIVES	ENDPOINTS (OUTCOME MEASURES)
Safety Assessments	
• AEs and SAEs*• Methemoglobin
Efficacy Assessments	
• Viral load• Viral infection• Symptoms 
• The primary safety measure is absence of device-related serious adverse events or any patterns of severity ≥ 2 device-related adverse events.*• Mean change in methemoglobin from baseline to Day 8/ET.• Time weighted average change in viral load from baseline by RT-qPCR from Day 1 to Day 8• Geometric mean viral load as measured in saliva on day 1, 3, 5, and 8 by RT-qPCR*• Proportion of subjects demonstrating viral load reduction $\geq 95\%$ by RT-qPCR (at each visit)*• Time to clearance of viral infection in saliva, defined as a negative test (Ct value ≥ 32) via RT-qPCR.• Proportion of subjects demonstrating clearance of viral infection, defined as a negative test (Ct value ≥ 32) via RT-qPCR on Day 8/ET.• Median time to alleviation of symptoms as measured by the time when all eight symptoms (cough, sore throat, nasal congestion, headache, chills/sweats,

OBJECTIVES	ENDPOINTS (OUTCOME MEASURES)

COVID-19 composite severity score.	muscle or joint pain, fatigue, and nausea) had been assessed by the subject as none (0) or mild (1).
Exploratory Assessment(s)	

Viral load by viral titer (at each visit)	
Geometric mean viral load as measured in saliva on day 1, 3, 5, and 8 by TCID₅₀ for replication competent virus.Geometric mean viral load as measured via oropharyngeal swab on day 1, 3, 5 and 8 by TCID₅₀ for replication competent virus.

*- indicates planned analysis for safety monitoring committee review between cohorts.

6.3 Scientific Rationale for the Study

RD-X19 through both direct and intermediate mechanisms, kills cell-free virus by as much as 99.99% and inhibits cell-associated replication of SARS-CoV-2 by 99.9% when measured at 24 hours after a single 5 minute treatment. Putative key virucidal mechanisms include upregulation of nitric oxide in epithelial tissue through increase of nitric oxide synthases (NOSs) and stimulation of the instantaneous release of the body's bound store of nitric oxide. Nitric oxide produced physiologically in epithelial tissues also induces and attracts effector cells of the innate immune system, including natural killer (NK) cells, neutrophils and macrophages to phagocytize virus-infected cells at the site of primary infection. The technology utilized by RD-X19 has been repeatedly demonstrated to provide high-level viral control in multiple, consistent, expert-laboratory *in vitro* studies. The mechanism of action, utilizing augmented innate immunity, presents an unprecedented opportunity for protection that is not specific antigen-directed or dependent.

6.3.1 Justification for Doses

In repeated experiments, including experiments conducted by third party external laboratories, it has been determined that the light emitted by the EmitBio™ RD-X19 device provides for potent antiviral activity against SARS-CoV-2. Reduction in cell-free virus of ≥ 1000 fold and inhibition of viral replication of $\geq 99\%$ have been observed in repeated experiments conducted by the sponsor and external expert laboratories.

[REDACTED] These repeated experiments, conducted in multiple labs with multiple cell types, along with years of medical use of licensed devices with comparable [REDACTED], support the doses proposed in this protocol for dose finding to achieve optimal efficacy and safety.

[REDACTED]

[REDACTED]

[REDACTED] The dosing schedule and duration has been selected to provide a reduction in viral load and symptomatic relief as rapidly as possible in COVID-19 patients while still maintaining an acceptable safety margin for each individual treatment session.

If patterns of \geq grade 2 device-related adverse events are observed, dosing will be reduced to one exposure/day for the remainder of treatment time. If serious or severe device-related adverse events are observed, further treatments at that dose will be terminated.

Strict safety oversight will provide rapid detection of significant device/dose-related adverse events warranting pausing or halting the trial.

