8.5 Device Discontinuation

8.5.1 Study Pausing Criteria

EB-P12-01 enrollment will be paused if any of the following events occur:

- Any subject experiences an SAE after use of the RD-X19 Device that is considered related to RD-X19.
- Any subject experiences laryngospasm, bronchospasm or anaphylaxis within 2 hours after use of the RD-X19 Device that is considered related to RD-X19.
- Two (2) or more subjects experience an allergic reaction such as generalized urticaria (defined as occurring at three or more body parts) within 72 hours after administration of light that is considered related to RD-X19.
- Three (3) or more subjects experience a Grade 3 AE (systemic and/or clinical laboratory abnormality), in the same SOC grouping of Preferred Terms based on the Medical Dictionary for Regulatory Activities (MedDRA) coding, considered to be related to RD-X19.

Enrollment may resume only after external safety review of the SAE/AEs that caused the pause to the study. Given the frequency of visits and the duration of the protocol, study device use may continue after assessing the safety and AEs for individual subjects at either regulatory scheduled or an unscheduled site visits.

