9.2.2 Solicited Adverse Events - Reactogenicity

Solicited AEs are anticipated AEs for which consistent collection of information is desired. Study clinicians will follow and collect resolution information for any reactogenicity symptoms that are not resolved during the active study period.

Solicited AEs (i.e., reactogenicity) will be collected by direct questioning of study subjects and recorded on the appropriate source document and e-CRF during the entire course of the study.

For this study, solicited AEs include:

- Illumination site Pain

- Illumination site Erythema
- Illumination site Edema/Induration
- Any other pain, redness, swelling or lesion of the oral mucosa

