9.2.9 Severity of Adverse Events

All AEs or SAEs will be assessed for severity, according to the toxicity grading scales provided at **Appendix 2**.

For AEs not included in the protocol-defined grading system, the following guidelines will be used to describe severity.

- Mild (Grade 1): Events that are usually transient and may require only minimal or no treatment or therapeutic intervention and generally do not interfere with the subject's usual activities of daily living.
- Moderate (Grade 2): Events that are usually alleviated with additional specific therapeutic intervention. The event interferes with usual activities of daily living, causing discomfort but poses no significant or permanent risk of harm to the research subject.
- Severe (Grade 3): Events interrupt usual activities of daily living, or significantly affects clinical status, or may require intensive therapeutic intervention. Severe events are usually incapacitating.

AEs characterized as intermittent require documentation of onset and duration of each episode. The start and stop date of each reported AE will be recorded on the appropriate e-CRF. Changes in the severity of an AE will be documented to allow an assessment of the duration of the event at each level of intensity.

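### For events that trigger an 8.5.1 pause, 6.3.1 ends treatment that 8.5.1 lets continue; and the 8.5.1 Grade 3 count leaves out the local reactions the trial solicits

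*Combined protocol and SAP*

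**What the plan says.** Protocol 6.3.1 (Justification for Doses) has two dosing rules. For a pattern of device-related AEs of grade 2 or higher, "dosing will be reduced to one exposure/day for the remainder of treatment time". For worse events: "If serious or severe device-related adverse events are observed, further treatments at that dose will be terminated".

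Protocol 8.5.1 (Study Pausing Criteria) pauses enrolment on any of four triggers, each considered related to the device: one SAE; one case of laryngospasm, bronchospasm or anaphylaxis within 2 hours; two allergic reactions within 72 hours; and "Three (3) or more subjects experience a Grade 3 AE (systemic and/or clinical laboratory abnormality), in the same SOC grouping of Preferred Terms". Enrolment resumes only after external safety review. On subjects already under treatment, 8.5.1 says that "study device use may continue after assessing the safety and AEs for individual subjects".

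Protocol 9.2.9 ties the two vocabularies together for events outside Appendix 2: "Severe (Grade 3): Events interrupt usual activities of daily living", among other features. Protocol 9.2.2 lists four solicited AEs: illumination-site pain, erythema and edema/induration, and "Any other pain, redness, swelling or lesion of the oral mucosa". On Phase I, 5.2.1 states: "By definition, all local site reactions were attributed to the device". The same sentence adds that all were mild and transient, with no increase in frequency on repeated dosing.

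The review between cohorts (4.1.2 and 6.1) counts related SAEs and Grade 3 AEs within one SOC and does not restrict them to systemic or laboratory events.

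**The concern.** The protocol has two sets of stopping rules whose scopes overlap, and they are not linked. Where a pause trigger is also a serious or severe device-related event, one section orders treatment to end and the other permits it after individual assessment. An investigator who continues dosing can cite 8.5.1, and one who stops can cite 6.3.1. Protection of subjects should not turn on which section is consulted.

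The second matter is what the enrolment pause is built to detect. Light is delivered to the mouth and throat, and the solicited AEs are the local effects expected there. Yet the only pause criterion based on a count of Grade 3 events leaves these effects out. For them, enrolment could go on without the external review that 8.5.1 demands for an equal number of systemic or laboratory events.

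**Working it through.** **Comparison of the rules.** The plan states no operating characteristic for its pausing rule, so there is no figure to reproduce. The texts set side by side give:

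| Related event | 6.3.1 | 8.5.1, enrolment | 8.5.1, device use | Conflict? |
|---|---|---|---|---|
| One SAE | Treatment at that dose ends | Paused | May continue after assessment | Yes |
| Three subjects, Grade 3 systemic or laboratory, one SOC | Treatment at that dose ends | Paused | May continue after assessment | Yes |
| One or two subjects, Grade 3, no other trigger | Treatment at that dose ends (see the plural below) | Not paused | Silent | No |
| Grade 3 local, not serious, allergic or airway, any number | Treatment at that dose ends | Not paused | Silent | No, but never a pause |

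The first two rows are the contradiction. The last row is the gap in the pause count. The 6.3.1 rule has no systemic or laboratory limit, so it covers the last row. Read at dose level it is stricter than a pause, because nobody can be newly treated at that dose. Read at subject level it leaves enrolment running.

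**Inputs for sizing the gap.**
- Active subjects: 20 per cohort (10.2); 36 × 2/3 = 24 if the enrolment allowed by Clarification Memorandum #2 is used at 2:1; 2 × 20 = 40 if the count runs over both cohorts, since 8.5.1 sets no per-dose limit.
- Risk p of a related local Grade 3 reaction (one SOC) per active subject: not in the documents. Assumed 2%, 5% and 10%.
- Phase I (5.2.1): 25 healthy volunteers aged 18 to 45; 23 AEs, 22 mild and one moderate, hence no Grade 3 event.

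**Is the assumed range compatible with Phase I?** With 0 of 25, the one-sided exact 95% upper limit is 1 − 0.05^(1/25) = 0.113. The chance of 0 of 25, (1 − p)^25, is 0.60, 0.28 and 0.07 at 2%, 5% and 10%. The range is not excluded, but its upper end sits close to the limit.

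**Chance that a count of three is reached if local reactions are included.** P(X ≥ 3) = 1 − (1 − p)^n − np(1 − p)^(n−1) − [n(n − 1)/2]p²(1 − p)^(n−2). For n = 20 and p = 0.05: 1 − 0.3585 − 0.3774 − 0.1887 = 0.075.

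| Active subjects | p = 2% | p = 5% | p = 10% |
|---|---|---|---|
| 20 | 0.7% | 7.5% | 32% |
| 24 | 1.2% | 12% | 44% |
| 40 | 4.6% | 32% | 78% |

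As 8.5.1 is now worded, the chance that its Grade 3 count pauses enrolment for these reactions is 0 at every risk.

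**The plural in 6.3.1.** The rule speaks of events, not of one event. If two affected subjects are needed, the case in which 6.3.1 acts and the 8.5.1 count does not is exactly two subjects: 190p²(1 − p)^18 = 5%, 19% and 29% for n = 20. If one is enough, it is one or two subjects: 33%, 57% and 56%.

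**The case against.** The strongest reply is that the sections can be read together. The permission in 8.5.1 follows the list of pause triggers, so it speaks only about what happens after a pause. It is permissive where 6.3.1 is mandatory, and a site that stops treatment complies with both. Section 6.3.1 ends treatment at a given dose, while 8.5.1 does not say that continued use is at the same dose, and once-daily dosing is available elsewhere in the plan. This narrows the conflict to pause-triggering events but does not remove it. No text says that continued use must be at a changed dose, excludes the affected subject, or gives one section precedence.

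A reader might infer a wider conflict: that after one or two related Grade 3 events 8.5.1 licenses further dosing that 6.3.1 forbids, with the 33%, 57% and 56% above as its size. The documents do not support this. Without a pause trigger 8.5.1 is silent, silence is not permission, and 6.3.1 governs alone.

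A reader might also infer that severe local reactions are uncontrolled. They are not. The 6.3.1 termination sentence covers them, and so do the rule on patterns of grade 2 or higher events (pattern is not defined), investigator removal under 8.5.3, regular review by the Medical Monitor and an external Data Monitoring Committee (6.1), and the SAP interim count of treatment-site reactions. What stands is that none of these pauses enrolment at a stated count, and that the interim count has no threshold and comes only once Cohort 1 is complete.

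Some relevant text cannot be seen: parts of 6.3.1 are redacted, Figure 1 is not shown, and the committee charter and the Appendix 2 grading scales are not in the documents. Any of these might settle the scope of the 6.3.1 rule or the grading of local reactions.

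**Conclusion.** Both parts hold in limited form.

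First, for serious or severe device-related events that also trigger an 8.5.1 pause, chiefly a related SAE, the protocol both ends treatment and permits it. It ranks neither rule and leaves the scope of 6.3.1 open between subject and dose cohort. This is a matter of wording and has no numerical size.

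Second, the Grade 3 pause count omits the type of harm that the trial solicits, whereas the protocol's own between-cohort criterion does not. The practical weight of the omission depends on 6.3.1: small if that rule stops the whole dose, larger if it stops only the affected subject. The pause probabilities rest on assumed risks, independence between subjects and a single SOC. With every Phase I local reaction mild and transient, severe ones are plausibly uncommon, though Phase I was done in healthy volunteers rather than COVID-19 patients. The point is a cheap improvement to make when the protocol is next amended, not a defect that undermines the trial.

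**What to change.** Three changes of wording in the protocol:

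1. In the 8.5.1 Grade 3 bullet, extend the parenthesis with *or illumination-site or oral-mucosal reaction as listed in 9.2.2*, keeping the count of three.
2. Begin the 8.5.1 clause on continued device use with *Subject to 6.3.1,*.
3. In 6.3.1, state whether termination applies to the affected subject or to the dose cohort.

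No new data, visits or committee are needed. The cost is a possible temporary enrolment pause for severe local reactions, lifted after the external review that 8.5.1 already provides. Its probability is the one tabulated above for a count of three, and it applies only where 6.3.1 has not already stopped that dose.
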